8.0 Standard Monitoring Plan

Safety

The primary study objective is to determine the MTD of the combination of lenalidomide, thalidomide and dexamethasone in relapsed/refractory MM patients. The type, frequency, severity, and relationship of adverse events to combination therapy will be ranked. Dose limiting toxicity (DLT) is defined previously and toxicity graded according to the NCI Common Terminology Criteria for Adverse Events v3.0. Dose adjustments will be made as described in the study design. The trial will be monitored by the PI with weekly meetings with the research nurse and data coordinator.

Safety Assessments

Safety assessments will consist of monitoring and recording all adverse events and serious adverse events, the regular monitoring of hematology, blood chemistry and urine values, regular measurement of vital signs and the performance of physical examinations.

9.1 Adverse Events

9.2 Serious Adverse Event (SAE) Definition

A serious adverse event is one that at any dose (including overdose):

- Results in death
- Is life-threatening¹
- Requires inpatient hospitalization or prolongation of existing hospitalization
- Results in persistent or significant disability or incapacity²
- Is a congenital anomaly or birth defect
- Is an important medical event³
- Suspected positive Pregnancy

¹ “Life-threatening” means that the subject was at immediate risk of death at the time of the serious adverse event; it does not refer to a serious adverse event that hypothetically might have caused death if it were more severe.

² “Persistent or significant disability or incapacity” means that there is a substantial disruption of a person’s ability to carry out normal life functions.

³ Medical and scientific judgment should be exercised in deciding whether expedited reporting is appropriate in situations where none of the outcomes listed above occurred. Important medical events that may not be immediately life-threatening or result in death or hospitalization but may jeopardize the patient or may require intervention to prevent one of the other outcomes listed in the definition above should also usually be considered serious. Examples of such events include allergic bronchospasm requiring intensive treatment in an emergency room or at home, blood dyscrasias or convulsions that do not result in inpatient hospitalization, or the development of drug dependency or drug abuse. A new diagnosis of cancer during the course of a treatment should be considered as medically important.

9.3 Adverse Drug Reaction Reporting

Toxicity will be scored using CTCAE Version 3.0 for toxicity and adverse event reporting. A copy of the CTCAE Version 3.0 can be downloaded from the CTEP homepage (<http://ctep.info.nih.gov>). All appropriate treatment areas have access to a copy of the CTCAE Version 3.0. All adverse clinical experiences, whether observed by the investigator or reported by the patient, must be recorded, with details about the duration and intensity of each episode, the action taken with respect to the test drug, and the patient’s outcome. The investigator must evaluate each adverse experience for its relationship to the test drug and for its seriousness.

The investigator must appraise all abnormal laboratory results for their clinical significance. If any abnormal laboratory result is considered clinically significant, the investigator must provide details about the action taken with respect to the test drug and about the patient's outcome.

9.4 Pregnancies

Pregnancies occurring while the subject is on lenalidomide or within 4 weeks after the subject's last dose of lenalidomide are considered expedited reportable events. If the subject is on lenalidomide, it is to be discontinued immediately and the subject is to be instructed to return any unused portion of the study lenalidomide to the Investigator. The pregnancy must be reported to Celgene Drug Safety within 24 hours of the Investigator's knowledge of the pregnancy by phone and facsimile using the SAE Form.

The Investigator will follow the subject until completion of the pregnancy, and must notify Celgene Drug Safety of the outcome as specified below. The Investigator will provide this information as a follow-up to the initial SAE.

If the outcome of the pregnancy meets the criteria for immediate classification as a SAE (i.e., spontaneous abortion [any congenital anomaly detected in an aborted fetus is to be documented], stillbirth, neonatal death, or congenital anomaly), the Investigator should follow the procedures for [Expedited Reporting of SAEs to Celgene](#) (i.e., report the event to Celgene Drug Safety by facsimile within 24 hours of the Investigator's knowledge of the event).

Any suspected fetal exposure to lenalidomide must be reported to Celgene within 24 hours of being made aware of the event. The patient should be referred to an obstetrician/gynecologist experienced in reproductive toxicity for further evaluation and counseling.

All neonatal deaths that occur within 30 days of birth should be reported, without regard to causality, as SAEs. In addition, any infant death after 30 days that the Investigator suspects is related to the *in utero* exposure to the study drug should also be reported.

In the case of a live "normal" birth, Celgene Drug Safety should be advised as soon as the information is available.

9.3.1 Celgene Drug Safety Contact Information:

Celgene Corporation
Drug Safety
[name]
[name]

Toll Free: [contact]
[contact]
[contact]
e-mail: [contact]

9.4 Investigator Reporting Responsibilities

The conduct of the study will comply with all FDA safety reporting requirements.

IND Annual Reports

If the FDA has granted an IND number, it is a requirement of 21 CFR 312.33, that an annual report is provided to the FDA within 60-days of the IND anniversary date. 21 CFR 312.33 provides the data elements that are to be submitted in

the report. The Annual Report should be filed in the study's Regulatory Binder, and a copy provided to Celgene Corporation as a supporter of this study as follows.

Celgene Corporation
Attn: Medical Development
[name]
[name]
[contact]

All adverse experience reports must include the patient number, age, sex, weight, severity of reaction (mild, moderate, severe), relationship to study drug (probably related, unknown relationship, definitely not related), date and time of administration of test medications and all concomitant medications, and medical treatment provided. The investigator is responsible for evaluating all adverse events to determine whether criteria for "serious" and as defined above are present. The investigator is responsible for reporting adverse events to Celgene as described below.

9.4.1 Expedited reporting by investigator to Celgene

Serious adverse events (SAE) are defined above. The investigator must inform Celgene in writing using any of the following forms, Celgene SAE form, MD Anderson SAE form, FDA 3500A or MEDWATCH form. of any SAE within 24 hours of being aware of the event. The date of awareness should be noted on the report. This must be documented on The written report must be completed and supplied to Celgene within 24 hours/1 business day at the latest on the following working day. The initial report must be as complete as possible, including details of the current illness and (serious) adverse event, and an assessment of the causal relationship between the event and the investigational product(s). Information not available at the time of the initial report (e.g., an end date for the adverse event or laboratory values received after the report) must be documented on a follow-up report. A final report to document resolution of the SAE is required. The Celgene protocol number (RV-MM-PI -0199) as well as the institutional protocol number (2008-0462) should be included on SAE reports (or on the fax cover letter) to Celgene. A copy of the fax transmission confirmation of the SAE report to Celgene should be attached to the SAE and retained with the patient records.

9.4.2 Report of Adverse Events to the Institutional Review Board

The principal Investigator is required to notify his/her Institutional Review Board (IRB) of a serious adverse event according to institutional policy.

9.4.3 Investigator Reporting to the FDA

Adverse drug reactions that are Serious, Unlisted/unexpected, and at least possibly associated to the drug, and that have not previously been reported in the Investigators brochure, or reference safety information document should be reported promptly to the Food and Drug Administration (FDA) by telephone or by fax.

Fatal or life threatening SAEs that meet the criteria for reporting to the FDA must be reported to the FDA within 7 calendar days after awareness of the event. All other SAEs that meet the criteria for reporting to the FDA must be reported to the FDA within 15 calendar days after awareness of the event. A clear description of the suspected reaction should be provided along with an assessment as to whether the event is drug or disease related.

9.4.4 Adverse event updates/IND safety reports

Celgene shall notify the Investigator via an IND Safety Report of the following information:

- Any AE associated with the use of study drug in this study or in other studies that is both serious and unexpected.

- Any finding from tests in laboratory animals that suggests a significant risk for human subjects including reports of mutagenicity, teratogenicity, or carcinogenicity.

The Investigator shall notify his/her IRB/EC promptly of these new serious and unexpected AE(s) or significant risks to subjects.

The Investigator must keep copies of all AE information, including correspondence with Celgene and the IRB/EC, on file.

10 Protocol Amendments/Deviations

10.1 Protocol amendments

Any amendment to this protocol must be agreed to by the Principal Investigator and reviewed by Celgene. Amendments should only be submitted to IRB/EC after consideration of Celgene review. Written verification of IRB/EC approval will be obtained before any amendment is implemented.

10.2 Protocol deviations

When an emergency occurs that requires a deviation from the protocol for a subject, a deviation will be made only for that subject. A decision will be made as soon as possible to determine whether or not the subject (for whom the deviation from protocol was effected) is to continue in the study. The subject's medical records will completely describe the deviation from the protocol and state the reasons for such deviation. In addition, the Investigator will notify the IRB/EC in writing of such deviation from protocol.

Non-emergency minor deviations from the protocol will be permitted with approval of the Principal Investigator.

10.3 Investigator responsibilities

Investigator responsibilities are set out in the ICH guideline for Good Clinical Practice (GCP) and in the US Code of Federal Regulations.

Investigators must enter study data onto CRFs or other data collection system. The Investigator will permit study-related monitoring visits and audits by Celgene or its representatives, IRB/EC review, and regulatory inspection(s) (e.g., FDA, EMEA, TPP), providing direct access to the facilities where the study took place, to source documents, to CRFs, and to all other study documents.

The Investigator, or a designated member of the Investigator's staff, must be available at some time during monitoring visits to review data and resolve any queries and to allow direct access to the subject's records (e.g., medical records, office charts, hospital charts, and study related charts) for source data verification. The data collection must be completed prior to each visit and be made available to the Celgene representative so that the accuracy and completeness may be checked.

11.1 Regulatory Considerations

11.2 Institutional Review Board/Ethics Committee approval

The protocol for this study has been designed in accordance with the general ethical principles outlined in the Declaration of Helsinki. The review of this protocol by the IRB/EC and the performance of all aspects of the study, including the methods used for obtaining informed consent, must also be in accordance with principles enunciated in the declaration, as well as ICH Guidelines, Title 21 of the Code of Federal Regulations (CFR), Part 50 Protection of Human Subjects and Part 56 Institutional Review Boards.

The Investigator will be responsible for preparing documents for submission to the relevant IRB/EC and obtaining written approval for this study. The approval will be obtained prior to the initiation of the study.

The approval for both the protocol and informed consent must specify the date of approval, protocol number and version, or amendment number.

Any amendments to the protocol after receipt of IRB/EC approval must be submitted by the Investigator to the IRB/EC for approval. The Investigator is also responsible for notifying the IRB/EC of any serious deviations from the protocol, or anything else that may involve added risk to subjects.

Any advertisements used to recruit subjects for the study must be reviewed and approved by the IRB/EC prior to use.

11.3 Informed consent

The Investigator must obtain informed consent of a subject or his/her designee prior to any study related procedures as per GCPs as set forth in the CFR and ICH guidelines.

Documentation that informed consent occurred prior to the subject's entry into the study and the informed consent process should be recorded in the subject's source documents. The original consent form signed and dated by the subject and by the person consenting the subject prior to the subject's entry into the study, must be maintained in the Investigator's study files.

11.4 Subject confidentiality

Celgene affirms the subject's right to protection against invasion of privacy. In compliance with United States federal regulations, Celgene requires the Investigator to permit Celgene's representatives and, when necessary, representatives of the FDA or other regulatory authorities to review and/or copy any medical records relevant to the study in accordance with local laws.

Should direct access to medical records require a waiver or authorization separate from the subject's statement of informed consent, it is the responsibility of the Investigator to obtain such permission in writing from the appropriate individual.

11.5 Study records requirements

The Investigator must ensure that the records and documents pertaining to the conduct of the study and the distribution of the study drug, that is copies of CRFs and source documents (original documents, data, and records [e.g., hospital records; clinical and office charts; laboratory notes; memoranda; subject's diaries or evaluation checklists; SAE reports; pharmacy dispensing records; recorded data from automated instruments; copies or transcriptions certified after verification as being accurate copies; microfiches; photographic negatives, microfilm, or magnetic media; x-rays; subject files; and records kept at the pharmacy, at the laboratories, and at medico-technical departments involved in the clinical study; documents regarding subject treatment and study drug accountability; original signed informed consents, etc.]) be retained by the Investigator for as long as needed to comply with national and international regulations (generally 2 years after discontinuing clinical development or after the last marketing approval). The Investigator agrees to adhere to the document/records retention procedures by signing the protocol.

- 24 Dunson DB, Neelon B: Bayesian inference on order-constrained parameters in generalized linear models. *Biometrics* 59: 286-95, 2003.
- 26 Bekele BN, Thall PF: Dose-Finding Based on Multiple Toxicities in a Soft Tissue Sarcoma Trial. *Journal of the American Statistical Association* 99:26-35, 2004.

Appendix A: Risks of Fetal Exposure, Pregnancy Testing Guidelines and Acceptable Birth Control Methods

Risks Associated with Pregnancy

The use of lenalidomide in pregnant females and nursing mothers has not been studied nor has the effect of the lenalidomide on human eggs and sperm. The risks to a fetus are not known. However, because lenalidomide is related to thalidomide, and thalidomide is known to cause severe birth defects, the following requirements must be observed.

All study participants must be registered into the mandatory RevAssist® program, and be willing and able to comply with the requirements of RevAssist®.

Females of childbearing potential (FCBP)[†] must agree to use two reliable forms of contraception simultaneously or to practice complete abstinence from heterosexual intercourse during the following time periods related to this study: 1) for at least 28 days before starting study drug; 2) while participating in the study; and 3) for at least 28 days after discontinuation from the study. The two methods of reliable contraception must include one highly effective method (i.e. intrauterine device (IUD), hormonal [birth control pills, injections, or implants], tubal ligation, partner's vasectomy) and one additional effective (barrier) method (i.e. latex condom, diaphragm, cervical cap). FCBP must be referred to a qualified provider of contraceptive methods if needed.

Before starting study drug:

Female Subjects:

- FCBP must have two negative pregnancy tests (sensitivity of at least 50 mIU/mL) prior to prescribing lenalidomide. The first pregnancy test must be performed within 10-14 days prior to prescribing lenalidomide and the second pregnancy test must be performed within 24 hours prior to prescribing lenalidomide (prescriptions must be filled within 7 days). The subject may not receive study drug until the Investigator has verified that the results of these pregnancy tests are negative.

[†] A female of childbearing potential is a sexually mature woman who: 1) has not undergone a hysterectomy or bilateral oophorectomy; or 2) has not been naturally postmenopausal for at least 24 consecutive months (i.e., has had menses at any time in the preceding 24 consecutive months).

Male Subjects:

- Must agree to use a latex condom during sexual contact with females of childbearing potential while participating in the study and for at least 28 days following discontinuation from the study even if he has undergone a successful vasectomy.

During study participation and for 28 days following discontinuation from the study:

All Subjects:

- If pregnancy or a positive pregnancy test does occur in a study subject or the partner of a male study subject during study participation, lenalidomide must be immediately discontinued.

Female Subjects:

- FCBP with regular or no menstrual cycles must agree to have pregnancy tests weekly for the first 28 days of study participation and then every 28 days while on study, at study discontinuation, and at day 28 following discontinuation from the study. If menstrual cycles are irregular, the pregnancy testing must occur weekly for

[figure not shown]
the first 28 days and then every 14 days while on study, at study discontinuation, and at days 14 and 28 following discontinuation from the study.

- In addition to the required pregnancy testing, the Investigator must confirm with FCBP that she is continuing to use two reliable methods of birth control at each visit.
- Pregnancy testing and counseling must be performed if a subject misses her period or if her pregnancy test or her menstrual bleeding is abnormal. Study drug treatment must be discontinued during this evaluation.

Male Subjects:

- Must agree to use a latex condom during sexual contact with females of childbearing potential while participating in the study and for at least 28 days following discontinuation from the study even if he has undergone a successful vasectomy.

Appendix B: Suggested Dose Modification Guidelines

NCI CTC Toxicity Grade	Day 2-14 of Cycle	≥Day 15 of Cycle
Grade 3 neutropenia associated with fever (temperature ≥ 38.5° C) or Grade 4 neutropenia	
 Hold (interrupt dose). Follow CBC weekly. If neutropenia has resolved to ≤ grade 2 restart at next lower dose level and continue the cycle until Day 21. 	
 Omit lenalidomide for remainder of cycle 
If neutropenia is the only toxicity for which a dose reduction is required, G-CSF may be used and the dose maintained for the next cycle at the investigators discretion.

Thrombocytopenia ≥Grade 3 (platelet count < 50,000/mm ³) *If patient starts at a platelet count of 50,000/mm ³ then follow these guidelines if platelets drop < 30,000 mm ³	
 Hold (interrupt dose). Follow CBC weekly. If thrombocytopenia resolves to ≤ grade 2 restart at next lower dose level and continue the cycle until Day 21. 	
 Omit lenalidomide for remainder of cycle
Non-blistering rash Grade 3 Grade 4	
 If Grade 3 hold (interrupt) dose. Follow weekly. If the toxicity resolves to ≤ grade 1 prior to Day 21 restart at next lower dose level and continue the cycle until Day 21. Discontinue lenalidomide study drug. 	
 Omit lenalidomide for remainder of cycle. Discontinue lenalidomide study drug.
Desquamating (blistering) rash- any Grade	
 Discontinue lenalidomide study drug. 	
 Discontinue lenalidomide study drug.
Erythema multiforme ≥ Grade 3	
 Discontinue lenalidomide study drug. 	
 Discontinue lenalidomide study drug.
Sinus bradycardia/ other cardiac arrhythmia Grade 2 ≥ Grade 3	
 Hold (interrupt) dose. Follow at least weekly. If the toxicity resolves to ≤ grade 1 prior to Day 21 restart at next lower dose level and continue the cycle until Day 21. Discontinue lenalidomide study drug. 	
 Omit lenalidomide for the remainder of the cycle. Discontinue lenalidomide study drug.
Allergic reaction or hypersensitivity Grade 2-3 Grade 4	
 Hold (interrupt) dose. Follow at least weekly. If the toxicity resolves to ≤ grade 1 prior to Day 21 restart at next lower dose level and continue the cycle until Day 21. Discontinue lenalidomide study drug. 	
 Omit lenalidomide for the remainder of the cycle. Discontinue lenalidomide study drug
Venous thrombosis/embolism ≥ Grade 3	
 Hold (interrupt) dose and start anticoagulation; restart at investigator's discretion (maintain dose level). 	
 Omit lenalidomide for remainder of cycle and start anticoagulation.

other non-hematologic toxicity assessed as LENALIDOMIDE-related \geq Grade 3	
 • Hold (interrupt) dose. Follow at least weekly. • If the toxicity resolves to \leq grade 2 prior to Day 21 restart at next lower dose level and continue the cycle until Day 21. 	
 • Omit lenalidomide for remainder of cycle.
Hyperthyroidism or hypothyroidism	
 • Omit lenalidomide for remainder of cycle, evaluate etiology, and initiate appropriate therapy. Restart lenalidomide next cycle (decrease dose by one dose level). 	
 • Omit lenalidomide for remainder of cycle, evaluate etiology, and initiate appropriate therapy. Restart lenalidomide next cycle (decrease dose by one dose level).

Dose modifications for Dexamethasone

Table 3: Dexamethasone Dose Modification		
NCI Toxicity Grade	Toxicity	Action
Grade 1/2	Dyspepsia, gastric or duodenal ulcer or gastritis	
 ▪ Treat with H2 blockers, sucralfate or omeprazole ▪ If symptoms persist decrease dose by 1 dose level as needed
\geq Grade 3	Dyspepsia, gastric or duodenal ulcer or gastritis	
 ▪ Hold until symptoms controlled ▪ Restart by decreasing dose by 1 dose level and add H2 blockers, sucralfate or omeprazole
\geq Grade 3	Edema	
 ▪ Decrease dose by one dose level ▪ Use diuretics as needed
\geq Grade 2	Confusion or mood alterations	
 ▪ Hold until symptoms resolved ▪ Restart dosing by decreasing dose down 1 dose level
\geq Grade 2	Muscle weakness	
 ▪ Decrease dose by 1 dose level ▪ If symptoms persist then decrease by dosing by 1 dose level as needed
\geq Grade 3	Hyperglycemia	
 ▪ Decrease dose by 1 dose level ▪ Treat with insulin or oral hypoglycemics as needed
\geq Grade 3	Acute pancreatitis	
 ▪ Discontinue subject from dexamethasone

Side effects associated with high-dose dexamethasone therapy include the following:

- Gastrointestinal: nausea, vomiting, anorexia, increased appetite, weight gain, aggravation of peptic ulcers
- Dermatologic: rash, skin atrophy, facial hair growth, acne, facial erythema, ecchymoses
- Genitourinary: menstrual irregularities, amenorrhea
- Neurologic: insomnia, euphoria, psychosis, headache, vertigo, depression, seizures, muscle weakness
- Cardiovascular: fluid retention, edema, hypertension, thrombophlebitis
- Ocular: cataracts, increased intraocular pressure, exophthalmos
- Metabolic: hyperglycemia, aggravation or precipitation of diabetes mellitus, adrenal suppression (with Cushingoid features), hypokalemia
- Hematologic: leukocytosis
- Other: osteoporosis, infection (including herpes zoster, varicella zoster, fungal infections, pneumocystis carinii, tuberculosis), muscle wasting, delayed wound healing, and suppression of reactions to skin tests.

Dexamethasone may be dose modified due to toxicity at the discretion of the treating physician as follows:

- Starting dose: dexamethasone 40 mg by mouth on days 1-4, 9-12 and 17-20 of each 28 day treatment cycle for cycle 1.

- During Cycle 2, 20 mg by mouth on days 1-4, 9-12, and 17-20.
For all cycles beyond 2:
- Dose level -1: dexamethasone 20 mg/m² po on Days 1, 8, 15 and 22.
- Dose level -2: dexamethasone 20 mg po on Days 1, 8, 15, and 22.
- Dose level -3: dexamethasone 20 mg po on Days 1 and 15.

Dose Modification Guidelines for Thalidomide:

1. Grade 1-2 AE the dose will be continued at the investigators discretion.
2. Grade 3 or higher AEs related to study drug, dose will be held until AE returns to grade 2 or less. If grade 3 AE occurs a second time the dose will be held until the AE decreases to grade 2 or less. Thalidomide will be restarted at 50% of previous dose. If grade 3 AE occurs a third time drug will be discontinued and the pt followed until the AE resolves or stabilizes.
3. For neurotoxicity for grade 2 toxicity or higher, hold drug until symptoms subside to baseline, grade 1 or less and then Thal may be restarted at 50% of previous dose. If neuropathy develops again with either Thal another 50% reduction can occur after symptoms resolve to 50 mg every day or every other day.
4. For grade 2 constipation Senna will be added to sodium docusate.
5. For somnolence the dose of Thalidomide should be held until symptoms resolve and then will be reduced 50%.

International Myeloma Working Group uniform response criteria:

Response Subcategory	Response criteria
sCR	CR as defined below plus Normal FLC ratio and Absence of clonal cells in bone marrow ^b by immunohistochemistry or immunofluorescence ^c
CR	Negative immunofixation on the serum and urine and Disappearance of any soft tissue plasmacytomas and \leq 5% plasma cells in bone marrow ^b
VGPR	Serum and urine M-protein detectable by immunofixation but not on electrophoresis of 90% or greater reduction in serum M-protein plus urine M-protein level < 100 mg per 24 h
PR	\geq 50% reduction of serum M-protein and reduction in 24-h urinary M-protein by \geq 90% or to < 200 mg per 24h If the serum and urine M-protein are unmeasurable, ^d a \geq 50% decrease in the difference between involved and uninvolved FLC levels is required in place of the M-protein criteria. If serum and urine M-protein are unmeasurable, and serum free light assay is also unmeasurable, \geq 50% reduction in plasma cells is required in place of M-protein, provided baseline bone marrow plasma cell percentage was \geq 30% In addition to the above listed criteria, if present at baseline, a \geq 50% reduction in the size of soft tissue plasmacytomas is also required
SD (not recommended for use as an indicator of response; stability of disease is best described by providing the time to progression estimates)	Not meeting criteria for CR, VGPR, PR or progressive disease

Abbreviations: CR, complete response; FLC, free light chain; PR, partial response; SD, stable disease; sCR, stringent complete response; VGPR, very good partial response.

^a All response categories require two consecutive assessments made at anytime before the institution of any new therapy; all categories also require no known evidence of progressive or new bone lesions if radiographic studies were performed. Radiographic studies are not required to satisfy these response requirements.

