6.2 Phase I Portion

To determine the MTD of the combination of thalidomide, lenalidomide and dexamethasone (LTD), with 4 dose levels planned. Dosing will start at doses of LTD that are intermediate intensity because of overlapping side effect profile of lenalidomide and thalidomide to determine the MTD and maximize the overall response rate of the regimen.

Table 6-1 Dose Levels to be studied

Dose Level	Assigned Therapy
Level -1	15 mg Lenalidomide daily on days 1-21 followed by 7-day rest every 28 days 50 mg Thalidomide daily 40 mg dexamethasone *
Level 1	15 mg Lenalidomide daily on days 1-21 followed by 7-day rest every 28 days 100 mg Thalidomide daily 40 mg dexamethasone *
Level 2	25 mg Lenalidomide daily on days 1-21 followed by 7-day rest every 28 days 100 mg Thalidomide daily 40 mg dexamethasone *
Level 3	25 mg Lenalidomide daily on days 1-21 followed by 7-day rest every 28 days 200 mg Thalidomide daily 40 mg dexamethasone

* Dexamethasone dosing for cycle 1-2: 40 mg days 1-4, 9-12, and 17-20; all subsequent cycles: 40 mg days 1,8, 15, 21

Dose Escalation

The first cohort of three patients enrolled into the study will receive dose level 1. A full safety evaluation will be conducted when these subjects have completed one cycle (28 days) of combination therapy.

Definition of DLT

A DLT will be defined as follows:

- Hematologic dose-limiting toxicity will be defined as either Grade 4 neutropenia lasting for ≥ 7 days in duration, any Grade 4 thrombocytopenia, or any Grade 5 hematologic toxicity. At least three patients in each cohort must be evaluable for hematologic toxicity.
- Non-hematologic dose-limiting toxicity will be defined as any Grade 3, 4 or 5 non-hematologic toxicity, with the specific exception of:
 - Isolated Grade 3 elevation of liver function tests (LFTs) without associated clinical symptoms, lasting for ≤ 7 days in duration.
 - Isolated Grade 3 elevation of amylase without associated clinical symptoms
 - Grade 3 hypocalcemia, hypokalemia, hypomagnesemia, hyponatremia, or hypophosphatemia which responds to medical intervention.

Definition of Maximum Tolerated Dose:

The MTD of the combination of lenalidomide, thalidomide and dexamethasone in multiple myeloma subjects shall be defined at the end of the trial, the dose with the smallest absolute value of (*posterior mean of pi-pT*) among all the tried doses *i* for which $T_i=0$ will be selected as the MTD.

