6.3 Phase II

Patients will be enrolled in the phase II portion of this study at the dosing regimen established in the phase 1 portion. Patients will be assessed for response each cycle of therapy.

An additional cohort of 10 patients with myeloma refractory to lenalidomide will be enrolled. This cohort of patients will be treated at the MTD regimen, with lenalidomide 25 mg po days 1-21 on a 28 day cycles and thalidomide 100 mg po daily. The dose of dexamethasone will be 40 mg po weekly.

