6.8.2 Dexamethasone Administration

For cycles 1-2 Dexamethasone will be given as a single daily oral dose of 40mg/day on Days 1-4, 9-12, and 17-20. If a dose of dexamethasone is missed or vomited, the patient should continue with the regular schedule of the drug at the next dose.

For cycles beyond 2, dexamethasone 40 mg/day will be given on days 1, 8, 15, and 22.

In the last cohort of 10 patients enrolled in the phase II, who were lenalidomide refractory, dexamethasone will be dosed weekly starting from cycle 1.

Dexamethasone should be taken at approximately the same time each day. Each dose of dexamethasone should be taken with food.

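### Appendix B's first dexamethasone reduction is dosed per m² against a flat 40 mg schedule, so at a body surface area of 2.0 m² or more it is no reduction, or an increase

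*Combined protocol and SAP*

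**What the plan says.** Section 6.8.2 fixes the scheduled dose in flat milligrams. For the first two cycles: "For cycles 1-2 Dexamethasone will be given as a single daily oral dose of 40mg/day on Days 1-4, 9-12, and 17-20". After that: "For cycles beyond 2, dexamethasone 40 mg/day will be given on days 1, 8, 15, and 22". The footnote to Table 6-1 in section 6.2 also uses flat doses, and section 6.3 says of the added lenalidomide-refractory cohort: "The dose of dexamethasone will be 40 mg po weekly".

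Appendix B then sets out three reduction levels for cycles after the second. The first is scaled to body size: "Dose level -1: dexamethasone 20 mg/m² po on Days 1, 8, 15 and 22". The second keeps those four days but reverts to a flat amount: "Dose level -2: dexamethasone 20 mg po on Days 1, 8, 15, and 22". The third holds that flat amount and halves the number of dosing days, to two in each cycle.

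Only the first of these is scaled to body size. No maximum dose, BSA cap or rounding rule goes with it.

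The dexamethasone modification table in the same appendix (Table 3) calls for a one-level step down for persistent Grade 1/2, or Grade 3 and above, dyspepsia, ulcer or gastritis. It does the same for Grade 3 and above edema, Grade 2 and above confusion or mood change, Grade 2 and above muscle weakness, and Grade 3 and above hyperglycemia. Section 6.11 makes these tables suggestions and leaves dose changes to the physician.

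**The concern.** A reduction ladder works only if each rung is lower than the one above it for every patient. Here the full dose and levels -2 and -3 do not depend on body size, but level -1 does. Whether the first step is a reduction therefore depends on how large the patient is.

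The step is used when dexamethasone is already causing harm, such as high glucose, mood change, muscle weakness, edema or gastric injury. A physician who follows the text literally for a large patient would leave the dose unchanged or raise it. Even where the step does lower the dose, the size of the cut varies with body size at this rung only, so patients recorded at the same level have had different degrees of reduction.

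**Working it through.** The plan states no figure to reproduce. The check compares level -1 with the dose it is meant to reduce.

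**Inputs**

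- Scheduled dose after cycle 2: 40 mg on days 1, 8, 15 and 22 (section 6.8.2), so 4 × 40 = 160 mg per cycle.
- Level -1: 20 mg/m² on the same four days (Appendix B), so 20 × BSA mg per dose and 80 × BSA mg per cycle.
- Level -2: 20 mg on the same four days, so 80 mg per cycle.
- Level -3: 20 mg on two days, so 40 mg per cycle.
- BSA: not given in the documents. I assume an adult range of 1.4 to 2.5 m².

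**Break-even.** Level -1 equals the scheduled dose when 20 × BSA = 40, so BSA = 40/20 = 2.0 m². The days are identical, so the per-cycle comparison breaks even at the same point (80 × 2.0 = 160 mg). This threshold comes from the protocol text alone.

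**Level -1 across the assumed range**

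| BSA (m²) | Level -1 per dose (mg) | Per cycle (mg) | Change from 40 mg |
|---|---|---|---|
| 1.4 | 28 | 112 | -30% |
| 1.6 | 32 | 128 | -20% |
| 1.8 | 36 | 144 | -10% |
| 2.0 | 40 | 160 | none |
| 2.2 | 44 | 176 | +10% |
| 2.5 | 50 | 200 | +25% |

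**Is 2.0 m² unusual?** With the common formula BSA = √(height in cm × weight in kg / 3600), which I assume because the protocol names none, BSA is 2.0 when height × weight = 4 × 3600 = 14,400. That is 14,400/170 = 84.7 kg at 170 cm, or 14,400/180 = 80 kg at 180 cm. These are ordinary adult sizes.

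**Shape of the ladder.** At 1.8 m² the first step removes 40 - 36 = 4 mg and the second removes 36 - 20 = 16 mg. At 2.2 m² the first step adds 4 mg and the second removes 44 - 20 = 24 mg.

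**Can the intended dose be recovered?** If the unit is a slip and the line should read 20 mg flat, level -1 becomes 20 mg on days 1, 8, 15 and 22, which is exactly level -2. A distinct flat level -1 on this schedule must lie strictly between 20 and 40 mg, and the documents do not say where.

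**The case against.** The case for treating this as a minor clarification has real substance.

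- **The guidance is optional.** Section 6.11 and the title and text of Appendix B all say so, and section 6.3.1 separately lets the physician interrupt or reduce doses. Someone who works out 40 or 44 mg while trying to reduce from 40 mg can go straight to level -2, a true 50% cut.
- **The failure is confined to one step.** For BSA between 1.0 and 2.0 m² the levels are correctly ordered, and levels -2 and -3 are reductions for everyone. The excess is 4 mg per dose at 2.2 m².
- **It applies only after cycle 2.** Compared with the 12 × 40 = 480 mg of each of the first two cycles, level -1 at 2.2 m² (176 mg) is still far lower.
- **Other measures apply.** The table holds dexamethasone first for some toxicities, adds treatment for others and stops the drug for acute pancreatitis.
- **The trial's conclusions are barely touched.** The phase I safety evaluation follows cycle 1, before these levels apply, so MTD selection is unaffected. The phase II response assessment after 4 cycles could be touched only through cycles 3 and 4, in large patients with a dexamethasone toxicity.

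All of this stands as a limit on severity. None of it makes the step correct when it is used, and the table directs physicians to use it. Nor can the line be dismissed as a typing slip that everyone will read the same way. Removing the unit leaves two identical levels, so different physicians could settle on different doses.

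**Conclusion.** The concern holds. As written, the first dexamethasone reduction after cycle 2 is not a reduction at a BSA of 2.0 m² and is an increase above it, reaching 10% at 2.2 m² and 25% at 2.5 m². Below 2.0 m² it is a cut of varying size, from 30% at 1.4 m² to 10% at 1.8 m².

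The 2.0 m² threshold needs no assumption. The range of BSA values, and the heights and weights that correspond to the threshold, are assumptions. The share of enrolled patients affected cannot be computed from the documents.

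This is a dosing-safety inconsistency that should be corrected. It is not a threat to the MTD determination, the sample size or the stopping boundaries. Its seriousness is limited by the advisory status of the tables, by the sound levels below it and by its restriction to cycles after the second.

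**What to change.** Amend the level -1 line in Appendix B so that the whole ladder uses flat milligrams and each level is below the one before it for every patient. On the present four-day schedule, that means a value strictly between 20 and 40 mg, chosen by the clinical team. If the team would rather have 20 mg as the first step, the per-m² line should be removed and the levels renumbered. It would also help to state the full 40 mg dose at the top of the ladder, so that the starting point of a one-level reduction is explicit.

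The cost is a one-line protocol amendment with the usual review and approval. No design quantity changes.

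Two separate dexamethasone discrepancies could be settled in the same amendment. Appendix B has "During Cycle 2, 20 mg by mouth on days 1-4, 9-12, and 17-20" where section 6.8.2 gives 40 mg in cycle 2, and the Table 6-1 footnote lists day 21 where section 6.8.2 lists day 22.
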